### **Provisions to Protect the Privacy Interests of Research Participants**

**Directions: Describe the steps that will be taken to protect research participants' privacy interests. (consider issues such as physical space, proximity to other, and participant preferences)**

*After eligibility is verified during phone screening by a team member, we will confirm with all study participants whether or not we can leave a voicemail message on their phone(s), and whether or not we can send mail to their home (in the event we cannot reach them by phone, and/or if they are randomized to the control group). We will ask if there are any disclosure concerns and make note if applicable in REDCap contact form. We will also ask study participants if they would like to be contacted for future research; we let them know there is no penalty to them if they do not wish to be contacted. Furthermore, we inform them that agreeing to be contacted does not obligate them to participate in future research, this only permits us to contact them. We will maintain a password-protected list on Box.com of individuals that have consented to be contacted for future research, along with their contact information and contact preferences. This list will be maintained by the Project Manager and may be shared with research team members, Co-Investigators, and/or other CWRU CREC-certified administrators on a case-by-case basis.*

*Privacy language is included in the informed consent form. Participants have the option of withdrawing from the study at any time and can request that no further information be shared about them from that point on. Participant names will not be shared in any report of the finding or with other study participants. Data collection interviews and intervention sessions will be conducted in a private setting (i.e. participant's home or other venue where others, including the persons with bipolar disorder, will not be present).*

*Confidentiality will be assured during all phases of the project by the following procedures.*

*Screening and Study ID numbers will be used for all caregivers. A list of screening and study ID numbers with identifying names, phone numbers, and addresses will be kept locked in password-protected files in Box.com and REDCap. The survey data will be kept in a separate*

*file from the data collected during the study and will only be accessible to the PI and research staff that need access to assure accurate follow-up in this longitudinal study. This identifiable information will be destroyed after all data have been collected.*

*Confidentiality issues will be addressed during training of research staff that will do the data collection and the interventionists. All data collected throughout the study, including signed consent forms, quantitative data using the REDCap system, HRV parameters, journals, emails, and field notes maintained by research assistants and interventionists will be stored in locked files and password protected computer databases only accessible to the PI, Co-I's, project manager, and research staff. These data will not include any identifiable information that may have been obtained during recruitment and screening. These measures have been used successfully to protect the rights of human subjects in our previous studies. In addition, we will implement the following specific strategies to protect data obtained from the journals or emails used by the caregivers.*

*1) Structured journal – caregivers receiving an intervention will be provided with a structured journal for their use during the four weeks between the first (T1) and second (T2) data collection interviews. They will be instructed to store the journal in a private place (known only to them) in their home during the four weeks. They will be directed to not use real names of friends, relatives, etc. within the journal entries; they may use alternative names if they wish. Interventionists will review the journals immediately upon retrieval (after the 28 day period) and if names are found, they will be blackened out and not appear within the transcribed text data files. The journals will be stored in a locked cabinet in the research office and the text files will be stored in a password protected computer database. Both the journal and text files will be kept for a period not to exceed 3 years. 2) Email - Individuals may use email to get more information about the study, and/or to contact staff once enrolled in the study. Email contacts and outcomes will be recorded generally on our contact forms, which use Study ID number and not names. If an email needs to be printed or otherwise saved, it will be securely downloaded to a PDF file, with names and other contact information redacted, and delete the original email message. The PDF file will be stored in the password protected computer file for a period not to exceed 3 years.*

## **Potential Benefit to Research Participants**

There is potential benefit to research participants.

Describe the potential benefits that individual research participants may experience from taking part in the research. Include the probability, magnitude, and duration of the potential benefits.

There is **no** direct benefit to research participants.

If no direct benefit, state the potential benefit to society or others. *Do not list compensation.*

## **Withdrawal of Research Participants**

**Directions: Describe the anticipated circumstances under which research participants will be withdrawn from the research without their consent. Also include the procedures that will be followed when a research participant withdraws or are withdrawn from the research, including partial withdrawal from procedures with continued data collection.**

N/A

*Participants have the option of withdrawing from the study at any time and can request that no further information be shared about them from that point on. If a study participant withdraws consent to participate in the study, a research team member will notify the project manager to complete end of study documentation.*

*The project manager will review cases regularly with research staff to determine which study participants should be withdrawn from the study. Research participants will be withdrawn from the research without their consent if they are non-responsive to phone calls, emails, texts, or letters and considered lost to follow up.*

*Data that were collected prior to a study participant's withdrawal will be de-identified and still be used in the data analysis for the study. After withdrawal, no further data will be collected for that participant.*

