Following the T1 data collection, the project manager will randomize each caregiver into one of four groups using Qminim, a secure online minimization program. Research assistants will be blinded as to which intervention arm caregivers are assigned to. The four groups are: 1) control group- no intervention; 2) usual care group- will receive bipolar education; 3) Self-management (SM)- need based, determined by baseline cut scores from T1- either bipolar education (ED), biofeedback (BF), resourcefulness training (RT), or no need; 4) SM-preference-based, caregiver selects intervention (ED, BF, RT, or no intervention). For SM-need, for example, caregivers scoring <70% on bipolar knowledge would be assigned to ED, < 97 on the resourcefulness scale to RT, and low HRV as determined by SDNN parameter for age and gender to BF. Those in the SM-need and SM-preference groups will perform one SM intervention (as listed above). Those in the usual care group will receive the same bipolar educational intervention as others in the SM-need or SM-preference groups. All interventions will take 4 weeks and these 4 weeks will occur between the T1 and T2 data collections; the T2 data collection is planned to occur 6 months after the initiation of the intervention. The T3 data

we are excluding pregnant women from joining the study (due to the variance in HRV data which would affect scoring for minimization), if someone becomes pregnant while they are enrolled in the study, we will not exclude them from the remainder of the study.

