Caregivers in the control group will receive a phone call (or email/text depending on their preferred method of contact) letting them know of their assignment; they will also have access to three interventions at the end of the study. Caregivers in the usual care, SM-need and SM-preference groups will receive training by a trained interventionist, which consists of a single face-to-face session in the caregiver's home/private venue. The session includes training/education via a voice-over PowerPoint presentation on iPad or laptop, and print materials to keep/review regarding the intervention. Other commonalities during the single session for ED, RT and BF are: 1) all caregivers will keep a structured journal, though the content will differ by intervention; journals will be collected after 4 weeks/ 28 days; 2) all will be taught to indicate day and time of the journal entry with the suggestion to do it at the same time each day; and 3) all will have the opportunity to complete a journal entry during the training session. During the 28-days after the initial session, all caregivers will: 1) perform the assigned intervention independently; 2) have print access to intervention content for review as they wish; 3) receive weekly follow-up from interventionists (3-5 minute phone call or email).

The ED and RT interventions involve providing educational information about bipolar disorder or teaching self-help (stress management, problem-solving) and help-seeking skills, respectively. BF training consists of the use of a hand-held device that shows the participant their changes in heart rate based on changes in their breathing patterns (as they relax); caregivers who need or prefer the biofeedback will be given a device to use for the study (for 28 days). Caregivers may use their intervention whenever and as often as they wish (i.e. self-tailoring). Dosing (number of times intervention is performed) and fidelity (using checklists) will be monitored. After 28 days, we will collect the BF hand-held devices and journals from all three interventions.

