*Individuals will be encouraged to continue with the interventions if they found them helpful (for BF, caregivers will have been given information on deep-breathing techniques without using a device). Caregivers who cannot be reached by phone or email for follow-up (either intervention or data collection) will have a letter sent to them if they have consented to having a letter sent to their home. Occasionally, calls will need to be made to study participants outside of the office (e.g., evenings/ weekends; when a research team member is working remotely/ in the field) or participants will request to be contacted by text. In these instances, the research team will use Google Voice, which allows users (research team) to set up a phone number through their CWRU email and is connected to their personal mobile phones. Calls and texts can be made to/ from the mobile phones while masking the actual phone number. When the research team is not working, calls will be directed to voicemail.*

*From Modification #8 (approved 03/06/2019)-- At the end of the T3 data collection, study participants will receive a brochure from each of the three interventions being researched, as well as an answer sheet for Caregiver Knowledge of Bipolar Disorder Questionnaire. Study participants who received an intervention will be asked a series of questions (up to 16) about their experience with, and opinion of, the intervention they received. Study participants who have already completed all three data collection sessions and have already agreed to be contacted for any questionnaire follow-up will be called and asked questions over the phone.*

Page 14 of 29

*The supplemental analysis will use baseline data (T1) to explore relationships among caregiver characteristics (race and gender), psychological stress (caregiver reactions and caregiving involvement), and physiological stress (heart rate variability time and frequency domains). De-identified baseline data from the demographic measures, psychosocial measures (caregiver reactions, caregiver involvement) and the HRV measurements will be used for this analysis.*

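### Staff may withdraw caregivers judged lost to follow-up, and data collection then stops for good, so T2 or T3 outcomes can be lost in people who never refused assessment

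*Combined protocol and SAP*

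**What the plan says.** Withdrawal of Research Participants has three linked parts.

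- **Who decides.** "The project manager will review cases regularly with research staff to determine which study participants should be withdrawn from the study".
- **Trigger.** "Research participants will be withdrawn from the research without their consent if they are non-responsive to phone calls, emails, texts, or letters". The sentence goes on to require that they also be judged lost to follow-up. No number of attempts, period or visit is attached to this.
- **Consequence.** "After withdrawal, no further data will be collected for that participant". Data already collected are kept and analysed. No re-entry is described. The template's directions for this section ask about partial withdrawal with continued data collection, and the answer does not address it.

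Study Design/Procedures supplies the context. Outcomes are measured at T1, T2 (6 months) and T3 (12 months). Caregivers receiving an intervention have a training session, weekly contacts over 28 days and collection of a journal or device. Controls get one notice of their assignment. On failed contact it says: "Caregivers who cannot be reached by phone or email for follow-up (either intervention or data collection) will have a letter sent to them", provided they agreed to mail. It also says that "the project manager will randomize each caregiver into one of four groups using Qminim"; only research assistants are described as blinded.

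Monitoring Study Safety has the committee review withdrawals, missing data and differential attrition by group. The Data Analysis Plan names a four-group by three-wave RMANOVA and no method for missing data.

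**The concern.** Being hard to reach is not the same as refusing assessment. A caregiver may ignore intervention calls for a month and still be willing to answer a survey at six or twelve months. The rule makes no such distinction, and its consequence is permanent.

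Two things are at stake. The first is information: later outcomes are given up that might have been obtained. The second is comparability of the randomised groups. Caregivers receiving an intervention have more scheduled contacts to miss than controls. The project manager, who leads the withdrawal review, also performs the randomisation and so presumably knows the arm. T2 is timed from the start of the intervention, but Research Participant Compensation times it from enrolment for controls. A caregiver assigned an intervention who is never reached for training therefore has no stated T2 date, whereas a control always has one.

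**Working it through.** The plan gives no loss rate, effect size or SD, so there is no figure of its own to reproduce. The check has two parts.

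**1. What the rule can cost, by time of withdrawal.** The last column assumes the usual RMANOVA behaviour, in which a case missing any wave is dropped. The plan does not state this.

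| Withdrawn | Outcomes forgone | If the caregiver were approached and reached instead |
|---|---|---|
| Before T2 (for example in the 28 days) | T2 and T3 | Complete case, if reached at both |
| After a missed T2 | T3 | T3 only; counts only in an analysis that keeps incomplete cases |
| Between T2 and T3 | T3 | Complete case |

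The first and third rows give a gain even under the planned RMANOVA. The second needs a change of analysis.

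**2. Illustrative size.** All inputs are assumptions: loss in an active arm p_a = 5%, 10% or 20%; loss in control p_c = 3%; equal arm sizes; and a gap δ = 0.5 SD between retained and lost caregivers, the same in both arms.

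In an arm losing a share p, the retained mean differs from the full mean by p × δ. So:

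- Bias of the contrast = δ × (p_a − p_c)
- SE inflation relative to no loss = √{[1/(1 − p_a) + 1/(1 − p_c)] / 2}

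| p_a | Bias (SD) | SE inflation |
|---|---|---|
| 5% | 0.5 × 0.02 = 0.01 | √[(1.0526 + 1.0309)/2] = 1.021 |
| 10% | 0.5 × 0.07 = 0.035 | √[(1.1111 + 1.0309)/2] = 1.035 |
| 20% | 0.5 × 0.17 = 0.085 | √[(1.2500 + 1.0309)/2] = 1.068 |

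To put the largest bias on a scale, assume 90 per arm (360/4; no allocation ratio is stated). The arms then keep 90 × 0.80 = 72 and 90 × 0.97 = 87.3. The standard error is √(1/72 + 1/87.3) = 0.159 SD, and the bias is 0.085/0.159 = 0.53 standard errors. With equal loss and equal δ the bias is zero and only precision suffers.

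These figures attribute all loss to the rule. Only caregivers who could later have been reached lose data because of it, and the documents do not allow their number to be estimated.

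**The case against.** The strongest reply is that the section describes ordinary handling of people who have disappeared. Withdrawal needs failed contact and a judgement of loss to follow-up, made in regular review with research staff. The committee watches attrition by group. Frequent contact may just as well improve retention in the active arms.

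Much of this stands, and it rules out several stronger readings that a reader might infer:

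- **That a single spell of silence triggers withdrawal.** The text permits this because it sets no threshold, but it does not prescribe it.
- **That a caregiver missed at T2 will not be approached at T3.** This holds only if staff have withdrawn the caregiver in between. The COVID-19 modifications allow an individual visit to be recorded as missed or collected later, although they do not alter the withdrawal rule.
- **That missed weekly calls lead to withdrawal.** The plan says only that a letter follows. Monitoring Study Safety lists leaving the study and refusing an intervention as separate matters. The step from one to the other is an inference.
- **That the active arms lose more, or lose the most distressed.** Neither is supported. Some members of the SM-need and SM-preference arms may have no intervention and so no weekly contacts. Usual care has training and weekly contacts like the self-management arms, so the contact argument bears mainly on comparisons with control.
- **That standard errors rise by 2.6%, 5.4% or 11.8%.** These follow from 1/√(1 − loss) and need both arms to lose the same share. They do not apply against a control arm losing 3%.

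What the reply does not meet is the consequence. Monitoring can reveal an imbalance but cannot recover outcomes that the protocol has stopped collecting.

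**Conclusion.** The concern holds as a defect of the rule, not as a demonstrated bias. The trigger is undefined, the review is led by someone who presumably knows the arm, and the result is permanent loss of later outcomes in people who may never have refused them. Differential loss by arm is possible, but its direction is unknown.

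The illustrated bias, 0.01 to 0.085 SD, is modest. It rests on the assumed loss rates, the assumed 0.5 SD gap and the attribution of all loss to the rule. The change is still worth making, because it is cheap and later analysis cannot replace outcomes that were never sought.

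**What to change.** Amend Withdrawal of Research Participants along these lines:

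- Only a caregiver's own request ends data collection. The existing right to withdraw is unchanged.
- Non-response to intervention contacts is recorded as non-adherence.
- Every randomised caregiver who has not asked to withdraw is approached at both T2 and T3. The contact schedule is the same in all four arms and respects stated contact preferences.
- Visits are timed from a date that exists for everyone, including those who never start an intervention.
- Loss to follow-up is declared only after the T3 attempts have failed.

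In the Data Analysis Plan, pair this with a primary analysis that uses partial follow-up, for example a likelihood-based mixed model, so that a recovered T3 counts when T2 is missing.

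The cost is a short amendment, a revised analysis paragraph, and a few extra calls, texts or letters per unreachable caregiver by existing staff.

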### **Alternatives to Participation**

**Directions: List other options to participation. If subjects will be compensated with extra course credit, the course instructor offering extra course credit must provide alternatives to earn extra course credit. The alternative assignment must require equal or less time and effort for the same amount of earned extra credit that you can earn through participation in research. If there are other available clinical treatments, what would be included if a subject continued on standard of care therapy. If there is a viable alternative you must list it in the consent.**

The alternative is for research subjects not to participate.

### **Costs to Research Participants**

There are **no** costs to research participants or their insurance companies (there are no clinical visits or billable procedures.) – *You may delete the rest of the section.*

1. Describe what costs research participants will be responsible for as a result of their participation in the research, including but not limited to: clinical services required by the protocol deemed billable to insurance, transportation to study visits, parking, costs of drugs, cost of therapy, lost broken or stolen devices, etc.

2. Explain who will be responsible for payment of provided services in the event of insurance denials.

3. List what procedures, drugs, devices, supplies will be paid by the study sponsor or covered by other funding. List the other funding source.

### **Research Participant Compensation**

There is no compensation for research participants – *please leave rest of this section blank*

There is compensation for research participants.

Describe the schedule, payment method, and payment total of any incentives or compensation that research participants will receive for participation in the research (e.g., gift cards or cash with amount, t-shirts, devices, bags, swag, etc.)

*Incentive will be provided as follows: completion of entire data collection at T1 (enrollment): \$20; T2 (6 months post intervention or from the date of enrollment if randomized to the control group): \$25; and T3 (6 months after second data collection): \$30 for a maximum total of \$75.*

**COVID-19 modification:** For T2 and T3 data collected remotely, study participants will receive a gift card mailed to them. The study will have 1-3 gift card vendor options to choose from/ the amount of the gift card will be \$25 for T2 and \$30 for T3.

There will be reimbursement for research participants.

Describe the schedule, payment method, and payment total of any reimbursement that research participants will receive for participation in the research (e.g., gift cards or cash with amount, etc.)

*If someone takes a bus or drives to CWRU or other community location to meet a research team member for T1, T2, T3, or an intervention meeting, we will reimburse that individual a 2-trip bus pass or parking voucher as appropriate.*

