## **Study Design/Procedures**

**Directions: 1) Describe the overall study design. 2) Provide a description of all study-related research procedures being performed, including the length of time involved. 3) Include procedures being performed to monitor research participants for safety or minimize risks. 4) Describe the source records including medical or educational records, which will be used to collect data about subjects.**

*The study is a four-year randomized controlled trial in Northeastern Ohio and includes a convenience sample of family caregivers of adults with bipolar disorder. After eligibility is verified during phone screening by team member, the consent forms will be reviewed verbally, questions about the study will be answered, and the study enrollment/first data collection appointment will be made.*

*There are three structured data collection time points (T1/enrollment, T2/ 6months after initiation of intervention, T3/ 12 months after initiation of intervention); these will be face-to-face with a research assistant, using a desktop, laptop, or iPad with secure REDCap software. During the enrollment and first data collection meeting, we will obtain informed consent from the caregiver. Caregivers will have time to ask questions about the study and review the consent form before signing it.*

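### As worded, control caregivers' T2 and T3 fall sooner after baseline than treated caregivers' do, and the primary RMANOVA takes no account of elapsed time (minor)

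*Combined protocol and SAP*

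**What the plan says.** Three places in the combined protocol and SAP time the follow-up assessments.

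- **Study Design/Procedures, overview of time points:** "T2/ 6months after initiation of intervention, T3/ 12 months after initiation of intervention". No control-group start is given there.
- **Study Design/Procedures, randomization and interventions:** "the T2 data collection is planned to occur 6 months after the initiation of the intervention". Also "All interventions will take 4 weeks and these 4 weeks will occur between the T1 and T2 data collections".
- **Research Participant Compensation:** "T2 (6 months post intervention or from the date of enrollment if randomized to the control group", then "T3 (6 months after second data collection".

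The intervention cannot start at baseline: "Following the T1 data collection, the project manager will randomize each caregiver into one of four groups". Under Consent Process, item 5, participants learn their group within roughly a month of the first session. Those in the three non-control arms then sign a second consent when their training session opens. No limit is given on the time from notice to training.

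Two arms may include caregivers who receive nothing. SM-need ends its list of outcomes with "resourcefulness training (RT), or no need", and in SM-preference the "caregiver selects intervention (ED, BF, RT, or no intervention".

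The Data Analysis Plan compares the four groups over three waves by RMANOVA, with no term for elapsed time. It also describes a linear trend as one in which scores reverse direction across waves.

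**The concern.** Control T2 is counted from enrolment. Treated T2 is counted from an event that comes after baseline, randomization, notice and a training appointment. T3 follows T2 by six months under the compensation wording, so an offset at T2 carries forward. If caregiver health drifts over time in everyone, treated arms accumulate a little more drift by each wave than control does. The group by time test cannot tell this from an intervention effect, and the bias can go in either direction.

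There is a practical side too. Monitoring Study Safety, item b, has session scheduling audited against the protocol, and the available text does not give one schedule for all four arms. The COVID-19 modification lets some T2 and T3 sessions wait for a later in-person date, so actual and nominal times separate further.

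**Working it through.** The plan states no figure to reproduce.

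**Dates.** The lag from T1 to the start of the intervention is not documented, so one month is assumed here for illustration.

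| Months since T1 | T2 | T3 |
|---|---|---|
| Control (from enrolment) | 6.0 | 12.0 |
| Treated, counted from start | 1 + 6 = 7.0 | 13.0 |
| Treated, counted from end of the 4 weeks | 1 + 28/30.44 + 6 = 7.92 | 13.92 |

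The offset from control is about 30 days on the first treated reading and 58 days on the second. Over assumed lags of 0 to 60 days it is 0 to 60 days, or 28 to 88 days.

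**Effect on the group by time test.** From the documents: target sample 360, four arms, three waves. Assumed: equal arms (360/4 = 90), no attrition, compound symmetry, correlation 0.6, drift 0.02 to 0.05 SD per month (the upper value is 0.6 SD per year, which is high), timing gap 0.25 to 1 month.

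- Spurious difference d = drift x gap at T2 and T3, and 0 at T1. Range: 0.02 x 0.25 = 0.005 SD to 0.05 x 1 = 0.05 SD.
- Centred sums of squares: group pattern (0,1,1,1) gives 0.75; time pattern (0,1,1) gives 0.667.
- Noncentrality = 90 x 0.75 x 0.667 x d²/(1 - 0.6) = 112.5 d².
- F with (4 - 1)(3 - 1) = 6 and (360 - 4) x 2 = 712 df, alpha 0.05.

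| Gap (months) | Drift (SD/month) | d (SD) | Correlation | Noncentrality | Rejection of a true null |
|---|---|---|---|---|---|
| 0.25 | 0.02 | 0.005 | 0.6 | 0.003 | 5.0% |
| 0.25 | 0.05 | 0.0125 | 0.6 | 0.018 | 5.1% |
| 1 | 0.02 | 0.02 | 0.6 | 0.045 | 5.2% |
| 1 | 0.05 | 0.05 | 0.6 | 0.281 | 6.1% |
| 1 | 0.05 | 0.05 | 0.4 | 0.188 | 5.7% |
| 1 | 0.05 | 0.05 | 0.8 | 0.563 | 7.3% |
| 1.92 | 0.05 | 0.096 | 0.6 | 1.04 | 9.5% |
| 1.92 | 0.05 | 0.096 | 0.8 | 2.07 | 14.9% |

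The last two rows apply only if the compensation wording means after the four weeks (1 + 0.92 = 1.92 months).

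**If untreated SM caregivers follow control timing.** With an assumed 20% or 50% of each SM arm on that schedule, the group sum of squares falls to 0.59 or 0.50, and the 6.1% becomes 5.9% or 5.7%. Usual care and SM would then differ by 0.2 x 0.05 = 0.01 SD or 0.5 x 0.05 = 0.025 SD.

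**Trend wording.** With linear weights (-1, 0, 1) and quadratic weights (1, -2, 1), means 0, 1, 2 give 2 and 0, while means 0, 1, 0 give 0 and -2. A pure reversal is all curvature and no linear trend, the opposite of the plan's sentence.

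**The case against.** The control start rests on one parenthesis in a section about payment. The two design passages agree with each other, and the payment wording may be loose shorthand for the start of the intervention. Nothing shows that it governs scheduling. Aligning treated arms to intervention start is also a legitimate choice. Lag, drift and correlation are all assumed. These points stand, and they keep the matter minor. They do not remove it: the payment passage is the only available text that says when control caregivers are assessed, and its enrolment start differs from the treated start on either reading.

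A reader might go further and infer that SM caregivers with no intervention have no assessment schedule at all. The documents do not support that. In the copy reviewed, the Study Design/Procedures paragraph breaks off just as it turns to T3 timing, and the lost text may supply a rule for them or for control. This is a point to check.

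A reader might also infer that control visits did take place early, or that the primary comparison is seriously biased. No actual lag or drift is documented, and over the main range the distortion is close to nothing. Nor is 9.5% a ceiling: it holds correlation at 0.6, and the same inputs at 0.8 give 14.9%.

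**Conclusion.** The concern holds as a minor inconsistency. As worded, control caregivers are assessed sooner after baseline than treated caregivers at T2 and, through the six-month spacing, at T3, while the RMANOVA assumes common waves. On the reading that counts from intervention start, the likely effect is at most 0.05 SD, with a rejection rate of 5.0 to 6.1% at correlation 0.6 and up to 7.3% at 0.8. Only the reading that counts from the end of the four weeks, combined with high drift and a one-month lag to the start, gives 9.5% to 14.9% (correlation 0.6 to 0.8). Every one of these figures depends on inputs that the documents do not give. The trend sentence is plainly wrong, but it leaves the contrast weights and tests unchanged. Its risk is a mislabelled result in the report.

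**What to change.** **Timing.**

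1. Reconcile the three passages to one outcome-assessment start for all four arms, either T1 or randomization. Alternatively, keep alignment to intervention start and give everyone without an intervention a matching notional start, such as the date of the assignment notice. State that the rule covers SM caregivers who receive nothing, after checking the full paragraph in Study Design/Procedures.
2. Apply the rule only to sessions not yet scheduled. The latest protocol date is 3/11/2021 and follow-up was already under way, so rescheduling across the board would add the very variation at issue. For sessions already held, state the rule actually used.
3. Report T1-T2 and T1-T3 intervals by arm.
4. Add one sensitivity analysis that keeps group by wave: a mixed model with unstructured within-person covariance and, as a time-varying covariate, the deviation of actual months since T1 from nominal wave time.

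A random-intercept model with group by linear months should not be used. It drops the wave structure and assumes that slopes do not vary between people. In a simulation with no true effect (90 per arm, visits at 0, 6 and 12 months, residual variance 0.4, 8,000 runs), it rejected 6.6% and 8.2% of the time at assumed slope SDs of 0.03 and 0.05 per month. RMANOVA with a Greenhouse-Geisser correction stayed near 5.0%.

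**Trend sentence.** Separately, correct the Data Analysis Plan to say that a linear trend is a steady overall rise or fall across waves, and a quadratic trend is curvature, that is, a change in the rate or direction of change.

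**Cost.** Wording in three passages, one corrected sentence, one derived variable and one extra model. Session dates are needed, and the documents do not explicitly say that they are kept. With a T1 or randomization start, time since intervention start will vary slightly within treated arms, and caregivers already enrolled may be on a different schedule from later ones.
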